9.3 Exploratory Endpoints and Analyses

The FAS will be used for all exploratory endpoint analyses unless stated otherwise.

Neurodegenerative Biomarkers

Neurodegenerative biomarkers including neurofilament light chain, total and phosphorylated tau protein, and amyloid- β (A β) peptides will also be collected at Screening and Day 14 of each treatment period. If data is available descriptive statistics of the neurodegenerative biomarkers and change from baseline to Day 14 will be summarized. Additionally, genetic biomarkers including APOE4, LRRK2, and GBA may be collected at Screening and descriptive statistics may be tabulated if numeric. All biomarker data will be listed.

Z-scores

Z-scores will be calculated for the observed values of select CANTAB, pVFT, and DSST endpoints using the formula: $z = (\text{observed value} - \text{normative mean}) / \text{normative SD}$. Normative means and standard deviations can be found in Appendix 3, and specifics on which parameters will be used in z-score derivations (ATT2BDM, PALTEA, RTIFMDRT, SSTSSRT, and VRMFR11D) are in section 9.2 in the CANTAB section. Z-scores will also be derived for the Alphabet and Category total scores of pVFT and the DSST total score. For the endpoints of PALTEA, RTIFMDRT and SSTSSRT, in which higher scores reflect poor performance, the sign of z-scores will be reversed by multiplying the calculated z-score by -1. Hence a positive z-score will reflect an outcome better than the norm and a negative z-score will reflect an outcome worse than the norm. In the case of the adaptive tracking test in the CANTAB, normative data are from prior studies conducted by CuraSen. For endpoints for which multiple norms are shown in Appendix 3, pooled estimates of the normal mean and SD, weighted by the sample size, will be used to calculate the z-scores. Z-scores for DSST will use norms based on the age of the subject. Normative data for the CANTAB, VFT, and DSST endpoints are summarized in Appendix 3. Normative data for the verbal fluency tests, DSST and most of the tests within the CANTAB are defined from published studies in which the tests were administered in an approximately similar manner as the CLIN-011 study. Normative data are based on untreated, approximately age matched cognitively normal populations, except for the Stop Signal Test where data are only available for a young adult population are available.

Summary statistics of z-scores and change from baseline for subjects with a baseline deficit will be presented for each of the 5 CANTAB parameters marked. Baseline deficit is defined as having a baseline z-score less than -0.5. Subjects with baseline values greater than or equal to -0.5 will not be summarized. Additionally, a mixed model approach will be used to evaluate treatment effect. The model will include change from baseline in z-score as the dependent variable, baseline as a covariate, treatment sequence, period, timepoint (i.e., Day 1: 3 hrs post-

hose, Day 7: 3 hrs post-dose, Day 14: 3 hrs post-dose), disease type, and treatment as fixed effects, and subject as a random effect. The least square means will be summarized, as well as the least square mean difference between treatments, where the corresponding p-value for this LS mean difference will be provided.

Summary statistics of z-scores and change from baseline for subjects with a baseline deficit for the two pVFT parameters will also be presented. Baseline deficit is defined as having a baseline z-score less than -0.5, and subjects with baseline values greater than or equal to -0.5 will not be summarized. Additionally, a mixed model with z-score change from baseline as the dependent variable, baseline as a covariate, treatment sequence, period, timepoint (i.e., Day 1, Day 7, Day 14), disease type, and treatment as fixed effects, and subject as a random effect will be analyzed, with the least square means, least square mean difference, and corresponding p-value will be provided.

Summary statistics of z-scores and change from baseline for subjects with a baseline deficit for DSST total score will be presented. Baseline deficit is defined as having a baseline z-score less than -0.5, and subjects with baseline values greater than or equal to -0.5 will not be summarized. Additionally, a mixed model with z-score change from baseline as the dependent variable, baseline as a covariate, treatment sequence, period, timepoint (i.e., Day 1, Day 7, Day 14), disease type, and treatment as fixed effects, and subject as a random effect will be analyzed, with the least square means, least square mean difference, and corresponding p-value will be provided.

10 PHARMACOKINETICS

Details regarding PK sampling, including scheduled timepoint and actual date and time of blood draws will be listed. Additional analyses of PK data will be summarized in a separate analysis plan.

11 SAFETY

11.1 Adverse Events

Adverse events (AEs) will be recorded from the time of randomization through end of study. AEs will also be assessed for severity, relationship to study drug, and seriousness. AEs will be considered treatment-emergent if their onset occurs following the date and time of first dose of CST-2032 or matching placebo up to the study completion date. Each TEAE will also be categorized according to the treatment period in which it occurs, in order to attribute and summarize an AE based on treatment received at time of event (i.e., during placebo or active treatment). Events that occur during the washout period between Treatment Period 1 and 2 will be attributed to the treatment received in Period 1, and events occurring after Treatment Period 2 up to the End of Study visit will be attributed to the treatment received in Period 2.

Any missing severity assessments will be assumed to be severe, missing relationship assessments will be assumed to be related, and missing seriousness assessments will be assumed as serious.

An overview of AEs will be produced, including counts and percentages of subjects with any incidences of: treatment-emergent AEs (TEAEs), serious AEs (SAEs), related AEs, unrelated AEs, AEs by maximum severity, AEs leading to treatment withdrawal and AEs leading to death.

Adverse events will be coded based on the Medical Dictionary for Regulatory Affairs (MedDRA 24.1) for reporting by system organ class (SOC) and preferred term (PT) in descending order of overall incidence.

Summaries of adverse events by SOC and PT will include the following types:

- TEAEs;
- SAEs; and
- Related AEs.

A summary of TEAEs by SOC, PT, and maximum severity will also be prepared.

A comprehensive listing of all AEs will be provided in a by-subject data listing. In addition, the following listings will be provided:

- SAEs;
- Related AEs; and
- AEs leading to study drug termination

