3. STUDY DESIGN

3.1. Clinical Trial Design

This is a Phase 2a, randomized, placebo-controlled, double-blind, crossover study to evaluate the safety, tolerability and effects of CST-2032 administered with CST-107 on cognition in subjects with MCI or mild dementia.

Approximately 60 subjects will be enrolled in a 2 period, 2-way crossover design following study eligibility confirmation during the screening period. Subjects will be randomly assigned to receive once daily doses of (a) 3 mg CST-2032 with 3 mg CST-107 or (b) both matching placebos in a randomized sequence (see [Study Schema](#)).

During each treatment period, subjects will receive 3 mg CST-107 or matching placebo on Day -1, followed by daily doses of CST-2032 (co-administered with CST-107) or matching placebo on Day 1 through Day 14. Each treatment period will be separated by a washout period of at least 7 days and up to 21 days. The washout period may be extended with prior approval by the CuraSen Medical Monitor.

All subjects will complete clinical, cognitive and pharmacodynamic assessments during each treatment period as indicated in the [Schedule of Events](#).

PK blood samples will be collected prior to, during and after study medication administration, as indicated in the [Schedule of Events](#).

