6.1.3. Reporting Serious Adverse Events

All SAEs that occur from time of informed consent until completion of the final visit, whether considered to be associated with the study medication or not, must be reported within 24 hours by telephone, e-mail, or fax to the Sponsor's Medical Monitor and/or Sponsor's designee using the appropriate contact details provided. The minimum information required for an initial report is:

- Sender of report (name, address of Investigator),
- Subject identification (subject number, NOT subject name),
- Protocol number,
- Description of SAE and date of onset,
- Relationship assessment,
- Date of visit and study visit number,
- Current status of subject.

However, whenever possible, all points on the SAE form should be completed and the form faxed or scanned and emailed to the Sponsor or designee. The site should also notify the Sponsor or designee by email or voicemail if the information was sent via facsimile. In addition, the event must be documented in the CRF.

It is recognized that it may be difficult to differentiate the relationship of an adverse event to CST-2032 or to CST-107 (nadolol). There is a long history of the clinical safety of nadolol and the dose of nadolol being administered in this study is less than 10% of the labeled starting dose for treatment of angina pectoris or hypertension (3 mg versus 40 mg). Therefore, unless the PI is confident in attribution of causality to CST-107 (e.g., for an AE that occurs prior to administration of CST-2032), all assessments of related AEs will be attributed to CST-2032 for expedited reporting purposes.

After receipt of the initial report, the Sponsor's Medical Monitor or designee will review the information and, if necessary, contact the Investigator to obtain further information for assessment of the event. The Sponsor or designee will be responsible for all information processing and reporting according to local legal requirements.

The Sponsor or designee will determine the SAEs requiring expedited reporting to regulatory agencies. The clinical trial site personnel are responsible for reporting these events to their Ethics Committee in accordance with applicable laws and regulations.

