8.2. Analysis Populations

The analysis populations are as follows:

Intent to Treat Set (ITT): All subjects who have signed informed consent and have been randomized to a treatment sequence. Subjects will be analyzed according to the treatment sequence assigned at randomization. The ITT will be the analysis set for disposition and select baseline characteristic analyses.

Safety Set: All subjects who received at least 1 dose of study drug (either CST-2032 or CST-107 or placebo). Subjects will be reported based on treatment and dose received. The Safety Set will be used for reporting of safety analyses.

Full Analysis Set (FAS): All randomized subjects who have taken at least 1 dose of blinded study drug (CST-2032+CST-107 or Placebo). Subjects will be analyzed according to the treatment assigned at randomization. The Full Analysis Set will be used for evaluating the cognitive endpoints, pharmacodynamic endpoints and selected secondary endpoints.

Per-Protocol Set (PPS): A subset of the Full Analysis Set who sufficiently complied with the protocol. Details of the evaluability criteria will be determined prior to study unblinding and specified in the SAP. The Per Protocol Set may be used for selected safety analyses.

Pharmacokinetic Set (PKS): All subjects in the Safety Set who have at least one valid plasma concentration assessment for CST-2032 or CST-107. Subjects will be analyzed according to the treatment received. The PKS will be the analysis set for PK concentration and PK parameter analyses.

Additional analysis populations may be defined in the Statistical Analysis Plan.

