8.7.1. Analysis of Adverse Events

Safety endpoints will be summarized by disease criteria, treatment, treatment sequence and overall using the Safety Set. Additional summaries may be performed by treatment, treatment sequence and/or period. A limited set of endpoints may also be summarized using other analysis populations.

All reported AEs will be coded using the Medical Dictionary for Regulatory Activities (MedDRA). Adverse event collection will begin during screening and will be collected up to 14 days after the last dose of study drug. All AEs collected on/after first dose of study drug will be considered treatment emergent (TEAE). Each TEAE will further be attributed to a treatment (CST2032+CST-107 or placebo) based on the AE start date. If a TEAE start date is prior to the first dose in Treatment Period 2, the AE will be attributed to the treatment received in Period 1. If a TEAE start date is on/after the first dose in Treatment Period 2, the AE will be attributed to the treatment received in Period 2.

An overall summary of the number and percentage of subjects experiencing TEAEs, serious AEs (SAEs), treatment-related AEs, AEs by maximum severity and AEs leading to treatment withdrawal will be provided. TEAEs, SAEs, and treatment-related AEs will be further summarized by MedDRA system organ class and preferred term and reported by treatment.

All AEs will be listed. Separate listings may be prepared for SAEs, AEs leading to study drug termination, and treatment-related AEs. Individual ECG results will be listed for each subject. Summaries of ECGs by treatment will include observed data and changes from baseline for each parameter including heart rate, QT, and QTcF. The number and percentage of subjects with abnormal ECGs will be summarized by treatment.

Additional analyses may be performed and will be described in the SAP.

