2.1 Changes to the Planned Analysis

There is still no adjustment of Type I error but hypotheses are not designated in priority order for hierarchical testing.

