7 GENERAL CONSIDERATIONS

7.1 Reference Dates

- Screening date is defined as the eCRF provided date on which a subject was screened for trial entry and informed consent was obtained.
- Treatment start date is defined as the date of first dose of CST-2032 or matching placebo. Each treatment period will have a treatment start date (i.e., in order to determine AEs occurring during a treatment). Subjects commence dosing of CST-107 or matching placebo 1 day earlier and this will be considered Day -1.
- Treatment end date is defined as the date of last dose of study drug.
- Safety data, such as AEs and laboratory assessments will use the treatment start date as a reference date.
- Study day will be based on treatment start date as a reference date.

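### Under the SAP, adverse events after the blinded Day -1 CST-107/placebo dose are not treatment-emergent in Period 1, and in Period 2 they can be counted in the opposite arm

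*SAP*

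**What the plan says.** SAP 11.1 gives the rule for treatment emergence: "AEs will be considered treatment-emergent if their onset occurs following the date and time of first dose of CST-2032 or matching placebo". SAP 7.1 matches it: "Treatment start date is defined as the date of first dose of CST-2032 or matching placebo". SAP 7.1 sets such a date in each period for the stated purpose of deciding which AEs fall within a treatment, and it notes that CST-107 or placebo begins one day earlier. SAP 11.1 then assigns washout events to the Period 1 treatment. It does not say when washout ends.

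Protocol 8.7.1 has a different anchor: "All AEs collected on/after first dose of study drug will be considered treatment emergent (TEAE". Its attribution switches to the Period 2 treatment under this condition: "If a TEAE start date is on/after the first dose in Treatment Period 2".

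Three other places bear on what counts as a dose and as a period:

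- The Safety Set in Protocol 8.2, repeated in SAP 5: "All subjects who received at least 1 dose of study drug (either CST-2032 or CST-107 or placebo".
- Protocol 3.1, repeated in SAP 4.1: "During each treatment period, subjects will receive 3 mg CST-107 or matching placebo on Day -1".
- Protocol 6.1.3, on attributing related events to CST-2032 by default: "unless the PI is confident in attribution of causality to CST-107 (e.g., for an AE that occurs prior to administration of CST-2032".

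SAP 2.1, the list of changes to the planned analysis, consists of one sentence: "There is still no adjustment of Type I error but hypotheses are not designated in priority order for hierarchical testing".

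**The concern.** Call the time from the Day -1 dose to the Day 1 dose the lead-in. It is randomized and blinded, and it is the only scheduled exposure to CST-107 alone. The protocol foresees AEs there that an investigator may attribute to CST-107. The SAP nevertheless treats the Period 1 lead-in as pre-treatment. A subject who takes only the Day -1 dose is then in the Safety Set but cannot have a TEAE.

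The Period 2 lead-in raises a different problem. The event remains treatment-emergent, but the SAP can be read as placing it in the Period 1 arm. In a two-treatment crossover that is always the wrong arm.

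Safety and tolerability is the primary endpoint, and TEAE tables by treatment are its main display. The summaries of SAEs and related AEs are not expressly limited to TEAEs, but they compensate only in part. SAP 11.1 gives an attribution rule for TEAEs only, so a Period 1 lead-in event has no stated arm in those tables.

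**Working it through.** The plan gives no figure to reproduce. The check applies each rule to every lead-in case and then counts.

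**Inputs.** About 60 subjects (Protocol 8.1); 1:1 allocation to two sequences (Protocol 7.2.1); 15 CST-107/placebo tablets per period (SAP 8.7); washout of 7 to 21 days and End of Study 7 to 12 days after the last dose (Schedule of Events). Assumption: all 60 are dosed in both periods, 30 per sequence.

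**Classification of a lead-in event**

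| Sequence | Period | Received in lead-in | Protocol 8.7.1, CST-107 as study drug | SAP 7.1 with 11.1 |
|---|---|---|---|---|
| Active then placebo | 1 | CST-107 | Active | Not a TEAE |
| Active then placebo | 2 | Placebo | Placebo | Can go to active |
| Placebo then active | 1 | Placebo | Placebo | Not a TEAE |
| Placebo then active | 2 | CST-107 | Active | Can go to placebo |

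**Windows.** 60 × 2 = 120. The 60 in Period 1 (30 CST-107, 30 placebo) cannot yield a TEAE under SAP 11.1. The 60 in Period 2 (30 and 30) are open to the opposite arm. If the SAP 7.1 reading is applied, none of the 60 CST-107 lead-ins is credited to active: 30 go to neither arm and 30 to placebo.

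**Effect per event.** These are upper bounds: the subject has no other TEAE in either arm, and each treatment has a denominator of 60.

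- Dropped Period 1 event: 1/60 = 1.7 percentage points on the between-treatment difference.
- Period 2 event in the opposite arm: a contribution of +1/60 becomes -1/60, so the change is 2/60 = 3.3 points.

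**Share of exposure and time**

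- Doses: 1/15 = 6.7% of CST-107 doses in a period.
- Day -1 dose to Day 14 dose: 1 + 13 = 14 days, as there is no Day 0.
- Period 1 attribution window: 14 + 7 = 21 to 14 + 21 = 35 days.
- Period 2 attribution window: 14 + 7 = 21 to 14 + 12 = 26 days.
- A one-day lead-in is 1/35 = 2.9% to 1/21 = 4.8% of the window.

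**Total effect.** The documents give no lead-in AE risk. If it were 1% to 10% per CST-107 lead-in (an assumption), the expected events would be 60 × 0.01 = 0.6 to 60 × 0.10 = 6.0. Half would be dropped and, on the adverse reading, half moved to placebo.

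**Appendix 1.** Its AE algorithm works on dates alone and uses a study drug start date that the SAP does not define. With the SAP 7.1 date, an event early on calendar Day 1, before dosing, is a TEAE in Appendix 1 but not in 11.1. If the date means the CST-107 start, Appendix 1 agrees with the protocol. SAP 7.4 invokes Appendix 1 only for missing dates, so it does not override 11.1.

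**The case against.** The strongest objection concerns Period 2. SAP 11.1 also attributes events by the treatment received when they occur, SAP 4.1 places the Day -1 dose inside the treatment period, and a washout between periods should end before that dose. On that reading the event goes to the correct arm. This stands as far as it goes, and it is why the point says only that misassignment can happen. But SAP 7.1 sets a Day 1 start in each period for this very purpose, so two programmers could assign the same event differently.

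Second, the term study drug is not used uniformly. The Protocol 5.1.2 heading dates it from after Day -1, and the Full Analysis Set pairs the two products. The Safety Set, however, governs the AE tables, and it names CST-107. Footnote 18 of the Schedule of Events likewise has study drugs given in the clinic on Day -1.

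Third, absence from SAP 2.1 is not in itself a breach, because Protocol 8.5 allows changes to be documented in the SAP and/or the study report. That is correct. The point is that a reader of the change list would not learn of this one.

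Fourth, the impact is small, and that stands too. The window is at most about a day, and the Period 1 exclusion applies to both arms alike. All AEs are still listed.

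**Conclusion.** The point holds. For Period 1 the exclusion follows directly from the text of SAP 11.1 and departs from Protocol 8.7.1, provided that study drug has its Safety Set meaning. For Period 2 the SAP is ambiguous, and one reading reverses the arm. The per-event sizes of 1.7 and 3.3 points are upper bounds at planned enrollment with everyone dosed in both periods. Neither the total size nor the direction of the effect can be computed from the documents. It should be fixed before database lock, because it concerns the definition behind the primary safety tables. It does not threaten the trial's conclusions as a whole.

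**What to change.** For AEs only:

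- In SAP 7.1 and 11.1, define a TEAE as onset at or after the date and time of the first dose of either blinded product, which is the Day -1 CST-107/placebo dose of Period 1.
- Switch attribution at the Period 2 Day -1 dose, and state that washout ends there.
- In the Appendix 1 AE algorithm, use this anchor under its own name, such as first blinded dose date. Leave the medication algorithm on the Day 1 reference of SAP 8.6.
- Treat a Day -1 onset without a time as after the dose, unless the record shows it was reported at the assessments preceding that dose. Report how many events this rule decides.

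If the Day 1 anchor is intended, list it in SAP 2.1 and add a table of lead-in AEs by CST-107 versus placebo.

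The cost is SAP wording and one derivation in the AE dataset. AEs are already recorded from randomization on Day -1, so no new collection is needed. The downside is the missing-time rule: some pre-dose Day -1 events may be counted as TEAEs or, in Period 2, moved out of the Period 1 arm. How often depends on whether onset times are captured. Protocol 6.1.2.2 asks only for the onset date, although the SAP's present date-and-time rule also needs a time.

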6.1.2.2. Relationship to Study Medication

The Investigator or designee, using clinical judgment, will assess the causality/relationship between each AE and the most recently administered study medication (i.e., whether there is a reasonable possibility that the drug caused the event) and record that assessment in the CRF.

Unrelated: The AE is clearly not related to the study medication. The AE is clearly explained by another cause, or exposure to the study medication has not occurred.

Related: The AE may be related to the study medication. The AE and administration of the study medication are considered reasonably related in time, but the AE is more likely explained by the study medication than another cause.

AE reporting will extend from randomization until completion of the End-of-Study Visit. AEs occurring after the end of the clinical trial must be reported if the Investigator considers there is a causal relationship with the study medication.

All AEs, regardless of the relationship to study medication, will be recorded in the CRF.

All reports should contain a brief description of the event, date of onset, date of resolution, severity, treatment required, relationship to study medication, outcome, and whether the event is classified as serious. Whenever possible, the Investigator should group signs or symptoms that constitute a single diagnosis into a single event term. For example, “cough, rhinitis, and sneezing” might be grouped together as “upper respiratory tract infection.”

A treatment-emergent clinically significant abnormal laboratory value should be recorded as an AE.

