7.2. Study Medication Dosing and Administration

The CST-2032 blister cards are designed for subjects to dispense 2 tablets on each dosing day according to the treatment the subject is randomized to receive and the treatment period in which they are participating, e.g.:

- 2 placebo tablets for administration of blinded placebo, or
- 1 tablet of 3 mg CST-2032 and 1 tablet of placebo for the blinded 3 mg dose.

The CST-107 blister cards or bottles allow subjects to dispense 1 tablet on each dosing day according to the treatment the subject is randomized to receive and the treatment period in which they are participating, e.g.:

- 1 placebo tablet for administration of blinded placebo, or
- 1 tablet of 3 mg CST-107 for the blinded 3 mg dose.

During each treatment period, subjects will receive CST-107 or matching placebo for 15 days and CST-2032 or matching placebo for 14 days:

- On Day -1, CST-107 or matching placebo will be administered in clinic after completion of all scheduled assessments.
- Study drug (CST-2032 and CST-107 or matching placebos) will be administered in clinic on Day 1 during which dispensing will be demonstrated to the subjects.

Subjects will receive a 1-week supply of study drug on Days 1 and 7 of each treatment period. CST-107 or matching placebo and CST-2032 or matching placebo are to be taken together each day during both treatment periods.

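### Washout AEs are charged to the Period 1 treatment with no day limit, so the post-dose AE window depends on period and scheduling and may attenuate the descriptive AE comparison; the AE collection window and TEAE start are also stated inconsistently

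*SAP*

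**What the plan says.** **Attribution.** SAP 11.1 says each TEAE is assigned "based on treatment received at time of event (i.e., during placebo or active treatment". It then sets the rule for the undosed time after Period 1: "Events that occur during the washout period between Treatment Period 1 and 2 will be attributed to the treatment received in Period 1". Onsets between the end of Period 2 and the last visit likewise go to the Period 2 treatment. Protocol 8.7.1 agrees, giving the Period 1 treatment every such event: "If a TEAE start date is prior to the first dose in Treatment Period 2, the AE will be attributed to the treatment received". Neither document caps the days after the last dose or plans a separate on-treatment AE table.

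**Length of the windows.** Under Protocol 7.2, "subjects will receive CST-107 or matching placebo for 15 days and CST-2032 or matching placebo for 14 days" in each period. Protocol 3.1 sets the washout at 7 to 21 days and adds: "The washout period may be extended with prior approval by the CuraSen Medical Monitor". No maximum is given for an extension. The Schedule of Events puts the End-of-Study visit 7 to 12 days after the last dose.

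**Collection window.** Protocol 8.7.1: "Adverse event collection will begin during screening and will be collected up to 14 days after the last dose of study drug". Protocol 6.1.2.2: "AE reporting will extend from randomization until completion of the End-of-Study Visit". SAP 11.1 agrees with 6.1.2.2. Protocol 6.1.3 separately collects SAEs from consent.

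**TEAE start.** Protocol 8.7.1 counts from the first dose of study drug, which is CST-107 or placebo on Day -1. SAP 11.1 and 7.1 count from the first dose of CST-2032 or placebo on Day 1.

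**The concern.** AE rates stand first in the primary endpoint, and Protocol 8.7 summarises that endpoint by treatment. SAP 11.1 aims to attribute events to the treatment being taken when they occur, yet during washout none is being taken. An event three weeks after the last dose counts the same as one during dosing.

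Two things follow. The number of days over which a subject can contribute an event depends on the period and on when Period 2 was booked. And if late onsets are mainly background, they add events to both treatments and pull the comparison toward no difference, which makes the active regimen look closer to placebo on safety.

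The collection and TEAE-start conflicts mean that two programmers could build different AE datasets. Under the SAP start dates, an event after the Period 2 Day -1 dose but before the Day 1 dose could be charged to the Period 1 treatment.

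**Working it through.** **Plan's own figure.** The synopsis gives a treatment/study period of 7 weeks: 14 + 21 + 14 = 49 days = 7 weeks. This reproduces with the 21-day washout.

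**Undosed share of the AE window.** Inputs: 14 days of CST-2032 or placebo per period (Protocol 7.2), washout w = 7 to 21 days (Protocol 3.1), follow-up f = 7 to 12 days (Schedule of Events).

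- Period 1, w/(14 + w): 7/21 = 33.3%; 14/28 = 50.0%; 21/35 = 60.0%.
- Period 2, f/(14 + f): 7/21 = 33.3%; 12/26 = 46.2%.
- Pooled over both periods, (w + f)/(28 + w + f): 14/42 = 33.3%; 33/61 = 54.1%.
- If the washout were extended to 28 days, for illustration: 28/42 = 66.7% in Period 1 and 40/68 = 58.8% pooled.

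**Possible attenuation.** The documents give no AE rates, so the rates here are assumptions: a constant background hazard λ of 0.01 or 0.02 per day, doubled on drug for 14 days and back to background immediately after the last dose. The proportion of subjects with at least one AE is P = 1 − exp(−(14hλ + λt)), with h = 2 on active, h = 1 on placebo, and t the undosed tail in days. With 1:1 sequences (Protocol 7.2.1) and no dropout, each treatment is half in Period 1 and half in Period 2, so P is averaged over the two tails.

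Example at λ = 0.02, tails of 21 and 12 days:

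- Active: 1 − exp(−0.98) = 62.5% and 1 − exp(−0.80) = 55.1%; mean 58.8%.
- Placebo: 1 − exp(−0.70) = 50.3% and 1 − exp(−0.52) = 40.5%; mean 45.4%.

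| λ per day | Tails after Periods 1, 2 (days) | Active | Placebo | Difference (points) | Ratio |
|---|---|---|---|---|---|
| 0.02 | 21, 12 | 58.8% | 45.4% | 13.3 | 1.29 |
| 0.02 | 7, 7 | 50.3% | 34.3% | 16.0 | 1.47 |
| 0.01 | 21, 12 | 35.9% | 26.2% | 9.6 | 1.37 |
| 0.01 | 7, 7 | 29.5% | 18.9% | 10.6 | 1.56 |

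Differences are taken before rounding. Against the longest unextended schedule, an equal 7-day tail recovers 2.7 points at 0.02/day and 1.0 point at 0.01/day. With a 7-day washout and 7-day follow-up it recovers nothing, because the windows are already equal.

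**Collection windows side by side.** Protocol 8.7.1 runs from screening to 14 days after the last dose. Protocol 6.1.2.2 and SAP 11.1 run from randomisation to the End-of-Study visit, 7 to 12 days after the last dose. The Schedule of Events starts AE assessment on Day -1, and no scheduled visit reaches day 14 after the final dose.

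**The case against.** Charging washout events to the preceding treatment is a defensible, pre-specified choice, and the two documents agree on it. The documents give no half-life for either drug, so early-washout events may well belong to the treatment just stopped. With 1:1 sequences the undosed time falls about equally on active and placebo. The primary endpoint is only summarised. SAP 11.1 also tabulates related AEs and lists all AEs, and Protocol 8.7.1 allows further summaries by period. ECGs, vital signs and laboratory values are summarised by visit, so this rule does not reach them. All of this stands, and it is why the attribution should be supplemented and not replaced. The optional period summaries, however, would not separate dosed from washout onsets.

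A reader might infer several stronger things that the documents do not support:

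- That 60% of the compared AE time is off drug. That figure is for Period 1 alone with a 21-day washout; the by-treatment tables pool both periods, giving 33% to 54% without extension.
- That the washout can be lengthened freely. Extension needs prior Medical Monitor approval; the accurate statement is that no maximum is given.
- That both treatments carry a 21-day tail throughout. After Period 2 the tail ends at 7 to 12 days.
- That late-washout events must be background because drug effects reverse within a day. Protocol 1.1.1 says this of heart rate, potassium and QTc under CST-2032 monotherapy, not of all AEs or of 14 days of the combination.

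**Conclusion.** The point holds as a cheap improvement to the safety tables and a necessary wording reconciliation. The AE windows are unequal by period (7 to 21 against 7 to 12 undosed days without extension) and depend on scheduling. This follows from the documents alone.

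The attenuation is conditional on late-washout events being mostly background. Under the assumed hazards it is modest on the risk difference (at most about 1.0 to 2.7 points relative to an equal 7-day tail, without extension) and clearer on the ratio (1.37 against 1.56, or 1.29 against 1.47). It is non-differential and touches a descriptive summary, so it should not be read as a biased test or lost power. "Undosed" here means no tablets taken, not absence of drug.

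The collection-window and TEAE-start conflicts need no assumption.

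**What to change.** 1. **SAP 11.1.** Keep attribution to the preceding treatment. In the TEAE summaries by treatment, add a split by onset: (a) from the first dose of the period to last dose + 7 days, the shortest follow-up both periods provide; (b) later washout or follow-up onsets, shown in a separate column under the same treatment.
2. **Collection window.** Reconcile Protocol 8.7.1 with Protocol 6.1.2.2 and SAP 11.1, leaving the SAE-from-consent rule in Protocol 6.1.3 intact.
3. **TEAE start.** Reconcile Protocol 8.7.1 with SAP 11.1 and 7.1, and define the first dose of a period accordingly, so that an event after the Period 2 Day -1 dose is not charged to the Period 1 treatment.

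The cost is one derived flag, one extra column and some wording. No event is dropped. The downsides are more output and that a late-onset drug effect would appear in the second column, so the two columns should be read together.
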